Randomization and Blinding: All eligible participants will be randomized to either the CCT or TAU group. Randomization tables will be prepared by the study statistician at the beginning of the study and assignments to CCT or TAU will be based on the randomization table. New participants will be allocated to the current group awaiting randomization. Once group membership reaches 6 participants, the group will be randomized by the statistician. We will employ a system of adaptive randomization, weighted to achieve the desired proportion of participants in each condition, managed by the statistician. Randomization will be implemented by the study coordinator in coordination with the statistician who will monitor randomization procedures. Because of the small sample size and number of study personnel in this pilot RCT, it might not be feasible to blind the assessor to participant group status if the assessor is also co-facilitating CCT groups with [name], though this type of blinding will be implemented if possible.

Data Analysis: Rates of recruitment, retention, and participation will be calculated, and we will compare participant characteristics at baseline by group (CCT vs. TAU). We will conduct intent-to-treat analyses to compare change from baseline to 3-month follow-up within and between groups.

Study Feasibility Analyses: Descriptive statistics will characterize the feasibility of recruiting and retaining Veterans. Recruitment will be deemed feasible if we successfully screen for eligibility 50% of Veterans referred to the study and enroll 75% of screened Veterans who meet all study inclusion criteria. Retention will be deemed successful if we achieve 80% completion for post-treatment assessments. Chi-square tests of association for categorical variables and t-tests for continuous variables will compare demographic and clinical characteristics of successfully versus unsuccessfully recruited and retained Veterans to identify characteristics of participants who may require more intensive recruitment or retention efforts in a future trial.

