In this pilot study, we will first examine descriptive statistics, and conduct tests of normality and homogeneity of variance for variables included in repeated measures analyses. We will examine missing data for all variables and dropout rates in order to plan for a future RCT. though will not conduct multiple imputation or other missing data techniques for this pilot study. We will, however, conduct intent to treat analyses, analyzing data from all randomized participants assigned to CCT versus TAU groups, rather than only including completers. Primary outcome analyses will be multilevel models to compare the change over time in cognitive, mental health, functioning, and QOL outcomes for Veterans in the CCT versus TAU groups. If the sample size is too small to run multilevel models, we will run alternative methods such ANOVAs which are more feasible with smaller samples. We will examine how much symptoms change, comparing changes across groups, and also examine clinically significant change in self-reported functional and clinical outcomes. We will compare the change in proportions of Veterans who fall within in "clinically significant impairment" ranges on objective cognitive performance measures before and after CCT versus TAU, characterizing cognitive functioning deficits according to cognitive domains. Because of the small sample size in this pilot RCT, these analyses will rely heavily on descriptive statistics including identifying individuals who score within clinically impaired ranges on objective testing, and who score above clinical cutoffs on self-report measures. Multilevel models or repeated measures analysis of covariance (ANCOVA) models will examine potential moderators including validity tests, service connection status and percent, number of sessions attended, comorbid mental health diagnosis such as PTSD, and demographic variables.

Study Population and Subject Identification/Recruitment

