Study setting, sample size, and recruitment feasibility: The proposed study is conducted at a single site. We propose to enroll at least 36, and up to 48, total Veterans in this pilot RCT. Because our primary purposes are to examine feasibility of this clinic-based research and acceptability to Veterans with PTSD and estimate effect sizes for a future fully powered RCT. achieving adequate statistical power is not a primary concern of this pilot clinical trial. Results from this pilot RCT with a sample size of 36 to 48, combined with comparisons to similar studies of CCT with other Veteran groups (e.g., those with mild TBI history), will provide adequate information on expected effect size to allow for estimations of statistical power for a future RR&D Merit proposal of a fully powered RCT. VHAPORHCS Mental Health and PTSD clinics will serve as primary sites for study recruitment, assessment, and intervention activities. We will work with the Public Affairs Office to post IRB approved study flyers in VHAPORHCS Mental Health and PTSD clinics and nearby elevators as well as the main hospital. The flyers provide information about the study and will help notify Veterans of the opportunity to participate in this study. Eligibility and recruitment procedures used to identify Veterans who report residual cognitive functioning deficits following recent (past year) treatment for PTSD at the Portland VA will be used to recruit Veterans for this pilot trial. Veterans who have participated in PTSD treatment and report cognitive functioning deficits on the Neurobehavioral Symptom Inventory (NSI; moderate cognitive symptoms or greater on any cognitive functioning item), will be recruited from the clinics.

CDW: If needed to achieve recruitment goals, we will also access the VA's Corporate Data Warehouse (CDW) and use ICD-10 codes to identify Veterans with recent (past year) Portland VA mental health or PTSD clinic treatment for PTSD. NSI data is also available for some Veterans in CPRS and Veterans with elevated NSI scores or neuropsychological evaluations

9

will be prioritized for recruitment. The CDW will be used to identify potentially eligible Veterans. The Veterans' clinicians will be contacted to ask them if they would like to refer these identified Veterans to the study. If the clinician wants to refer a Veteran to the study, this will be documented and the IRB approved recruitment procedures for a referred Veteran will then be followed.

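### The ANOVA fallback and the repeated-measures ANCOVA, if run over all three visits with no missing-data method, cannot deliver the promised intent-to-treat set

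*Combined protocol and SAP*

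**What the plan says.** The Data Analysis paragraph sets the contrast: "We will conduct intent-to-treat analyses to compare change from baseline to 3-month follow-up within and between groups". The Clinical and Functional Outcome Analyses section then makes four statements.

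- On the analysis set, it commits to "analyzing data from all randomized participants assigned to CCT versus TAU groups, rather than only including completers".
- On missing data, it "will not conduct multiple imputation or other missing data techniques for this pilot study".
- On the model: "Primary outcome analyses will be multilevel models to compare the change over time". If the sample is too small for that: "If the sample size is too small to run multilevel models, we will run alternative methods such ANOVAs which are more feasible with smaller samples".
- On moderators: "Multilevel models or repeated measures analysis of covariance (ANCOVA) models will examine potential moderators".

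No number or convergence rule defines too small. The section does not say which visits an ANOVA would use, or how a Veteran with a missing visit would enter it. Enrollment and Assessment Procedures schedules three assessments: baseline, about 3 months (post-treatment) and 6 months. On retention, Study Feasibility Analyses says: "Retention will be deemed successful if we achieve 80% completion for post-treatment assessments".

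**The concern.** The first two statements are compatible under a multilevel model fitted by likelihood, because such a fit uses each visit that was observed and needs no imputation. They are not compatible with a conventional repeated-measures ANOVA or ANCOVA over three visits, which needs a complete row for each person. A Veteran seen at baseline and post-treatment but not at 6 months would be deleted, along with a post-treatment score that was in hand. The retention procedures make a deliberate effort to assess Veterans who stop treatment, and this deletion would waste any partial data they provide.

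At stake is Aim 2. The effect sizes from this pilot feed the sample size of the next trial, and a result from assessment completers could be reported under an intent-to-treat label.

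**Working it through.** **Inputs.** Total sample: "We propose to enroll at least 36, and up to 48, total Veterans in this pilot RCT" (Study setting, sample size, and recruitment feasibility). Arms: 4 to 5 CCT groups of 6 and 12 to 18 TAU (Inclusion/Exclusion Criteria). The head count adds up: 4×6 + 12 = 36 and 5×6 + 18 = 48. Retention r: 80% as the success criterion; above 90% in earlier CCT trials (Participant retention/Dropout Minimization). The plan gives no alpha, power, SD or effect size, so it has no power figure to reproduce.

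**Veterans kept.** Two visits (baseline and post-treatment): N×r. Three visits, assuming the same proportional loss again by 6 months: N×r².

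| N | r | Two visits | Three visits |
|---|---|---|---|
| 36 | 0.80 | 28.8 (7.2 lost) | 23.0 |
| 48 | 0.80 | 38.4 (9.6 lost) | 30.7 |
| 36 | 0.90 | 32.4 (3.6 lost) | 29.2 |
| 48 | 0.90 | 43.2 (4.8 lost) | 38.9 |

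The loss at post-treatment is common to every method. What the three-visit requirement adds at 80% is 28.8 − 23.0 = 5.8 Veterans at N = 36, and 38.4 − 30.7 = 7.7 at N = 48. A TAU arm of 12 falls to 9.6 and then 7.7. Some missingness is close to certain: even at 90%, the chance that at least one of 36 misses post-treatment is 1 − 0.9³⁶ = 0.98, assuming independence.

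**Precision.** Approximate 95% half-width of a standardised difference: 1.96×√(1/n₁ + 1/n₂).

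- 24:12, nobody missing: 0.69
- 19.2:9.6, two visits at 80%: 0.77
- 15.4:7.7, three visits at 80%: 0.87

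For 30:18 the same steps give 0.58, 0.65 and 0.73.

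**Which models delete.** In a constructed dataset of 36 Veterans with 7 missing the 6-month visit, 29 were complete for a three-visit ANOVA. A mixed model used all 36 and 101 of 108 rows.

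**Bias, by simulation.** Assumptions: true post-treatment effect 0.40 SD, equal correlation between visits, 20% missing the 6-month visit only, and loss driven by poor 3-month change (log-odds 1 per SD unit) where stated.

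| Setting | All observed post-treatment | Three-visit completers |
|---|---|---|
| Driven loss in CCT only, r = 0.6 | 0.40 | 0.54 |
| Same, correlation 0.5 / 0.7 | 0.40 | 0.57 / 0.51 |
| Same, r = 0.6, 10% loss | 0.40 | 0.475 |
| Same mechanism in both arms, r = 0.6 | 0.40 | 0.40 |

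(Here r is the visit correlation.) A second version, with true effect 0 and CCT loss driven by the 3-month score rather than the change, gave a completer bias of 0.07 to 0.12 SD in favour of CCT, and about 0.00 for a likelihood estimate.

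**What a per-visit fallback does not repair.** If the same CCT-only mechanism removes the 3-month visit itself (20% loss, correlation 0.6), the change contrast is 0.54 and a baseline-adjusted ANCOVA on those observed gives about 0.51, against a true 0.40.

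**What the extreme case would mean.** With n per arm = 15.7/d² (two-sided 5% and 80% power, both assumed), d = 0.40 needs 98 per arm and d = 0.54 needs 54.

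**The case against.** The strongest reply is that this concerns a contingency. The multilevel model is already the primary analysis, and it should be estimable at 36 to 48: a random-intercept model fitted to 200 simulated 24:12 datasets, with about 20% lost at each follow-up, converged every time. That stands. A reader might infer that the trial's main result will be a completer analysis, or that the fallback is likely to be used; the documents support neither.

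Second, the plan never says that the ANOVA spans three visits. An ANOVA of the baseline-to-3-month change in the Data Analysis paragraph would lose nobody for missing only the 6-month visit. That stands too, and is why the point is conditional. Nor does the plan rule out the three-visit form, and the moderator option is explicitly repeated-measures. That ANCOVA is offered for moderators, however, and is not part of the small-sample fallback.

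Third, it is tempting to say that the fallback would overstate CCT and shrink the next trial from 98 to 54 per arm. That needs outcome-driven loss confined to CCT; when both arms share the mechanism there is no bias. The outcome section itself says a small pilot's effect size should not be the sole estimate and will be set beside the mild-TBI trial. The 80% figure is a success threshold rather than a forecast, and earlier trials did better.

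Finally, completer here means assessment completer. Veterans who stop treatment are still invited to assessments, and an ANOVA keeps them if they attend.

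**Conclusion.** The inconsistency is real but conditional. The stated analysis set, the exclusion of missing-data techniques and a three-visit ANOVA or ANCOVA cannot all hold once any visit is missed. The first-choice model is unaffected if it is fitted by likelihood, which the plan does not state.

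At 80% retention, with the same loss assumed again by 6 months, the three-visit requirement would discard a further 6 to 8 Veterans beyond those already missing at post-treatment, leaving about 23 to 31. The half-width at N = 36 would widen from 0.77 to 0.87 SD. That cost in precision arises whatever the reason for loss. Bias of up to about 0.14 SD at correlation 0.6 is an illustration that depends on loss differing by arm in its relation to outcome; the documents give no evidence on that either way. This is worth correcting because it is cheap and Aim 2 rests on these estimates. It does not undermine the primary analysis.

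**What to change.** In Clinical and Functional Outcome Analyses:

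1. State that the multilevel model is fitted by likelihood to every observed visit of every randomised Veteran, including those who stopped treatment, with a small-sample degrees-of-freedom correction. Note that this relies on data being missing at random given what was observed.
2. Use the same model for the moderators in place of repeated-measures ANCOVA.
3. If the model cannot be fitted, replace the ANOVA with a separate ANCOVA at each visit (score on arm and baseline) using everyone observed at that visit, so that the post-treatment contrast never requires the 6-month visit.
4. Label that fallback an observed-case analysis, not intent-to-treat.
5. Report by arm and visit the numbers randomised, analysed and excluded for missing data.

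The cost is a few sentences and no new data. The fallback gives per-visit estimates instead of one omnibus test, and it still omits Veterans unseen at a visit from that visit's estimate. It therefore limits the loss without restoring intent-to-treat, which is why the label and the counts matter.

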Intervention: TAU will consist of routine, weekly mental health psychotherapy as all participants must have a referring mental health provider to be eligible for this pilot RCT. The CCT rehabilitation model aims to teach individuals strategies that allow them to work around cognitive deficits. CCT provides training in compensatory attention and learning/memory skills, formal problem-solving strategies applied to daily problems, and the use of external aids, such as calendar systems and assistive devices to promote completion of daily tasks ([name] et al., 2016). CCT sessions consists of interactive didactic information and discussion, and activities that introduce a variety of cognitive strategies and external aids. Participants are given a copy of the treatment manual and a paper calendar or day planner if requested, or they may request training on a smartphone or electronic calendar system instead. They will receive extensive graduated training in and practice with their chosen calendar system across sessions with a focus on how the day planners can facilitate the use of compensatory strategies taught each week. [name] will supervise the CCT groups run by the study coordinator, co-facilitating early groups as needed for training purposes. They have an ongoing relationship with local psychology doctoral programs which may provide clinical trainees who may provide supervised group facilitation. The current CCT Treatment Manual ([name], [name], et al., 2016) is included as an Appendix, though aspects of structure and content will be changed before this pilot RCT for PTSD to tailor the intervention to PTSD rather than TBI. We have successfully tailored CCT to other similar Veteran populations in the past, and we expect to be able to refine it for Veterans with PTSD prior to CDA initiation. We have also had success training a variety of master's level research associates and providers to administer the intervention, and similar training and fidelity monitoring protocols (e.g., recorded sessions, 20% random fidelity checks) previously utilized by Drs. [name], [name], and [name] will be implemented in this proposed efficacy study. The following table outlines the CCT structure and content.

Table of CCT for PTSD Session Content				
Session	Major Concepts	Examples of Strategies	Session Activities	Home Exercise
1	Intro and PTSD/cognitive functioning psychoeducation	Creating a "home" for important items	Day planner use	Finding a home for the day planner

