intervention fidelity; and maximize participant retention. Detailed records on recruitment, session attendance, and homework completion will be kept throughout the intervention. Consistent with Consolidated Standards of Reporting Trials (CONSORT) guidelines, we will obtain data to determine (1) the number of participants who reported moderate or greater symptom ratings, or who have impairments in one or more cognitive domain, from the baseline assessment; (2) the number of participants referred to the study, (3) the number of participants screened by research staff for study eligibility, and (4) the number enrolled in and completing all aspects of the study including treatment sessions and assessments. We will ascertain reasons for unsuccessful recruitment, ineligibility, and unsuccessful enrollment of eligible Veterans. In addition, we will collect data on the intensity of outreach needed to recruit and enroll participants (e.g., number of phone calls required before Veterans complete eligibility screening, number of "no shows" for eligibility screening appointments) and length of time between initial recruitment attempt, eligibility screening, and completion of the pre-intervention assessment. Participant Retention will be measured by the proportion of participants who complete follow-up assessments within two weeks of the target date. Treatment satisfaction will be assessed by the Client Satisfaction Questionnaire (CSQ8).

Functional and Clinical Variables: We will use similar assessment procedures as in the Aim 1 study to assess cognitive and functional domains most strongly associated with PTSD (details listed in the table below). We will examine sleep and mental health symptoms (including PTSD and depression) not directly targeted by CCT to examine comparability to TAU. Assessments will take approximately 1.5 hours and will occur at baseline, post-treatment, and 6-month follow-up for both groups.

Measure	Construct Assessed			
Objective Cognitive Functioning (Neuropsychological Tests)				
Test of Premorbid Functioning (ToPF)	Verbal abilities; estimate of premorbid cognitive functioning			
California Verbal Learning Test (CVLT-II; Delis et al., 2000)	Verbal learning and memory, forced choice validity			
Wechsler Adult Intelligence Scale (WAIS-IV) Digit Span & Coding subtests (Wechsler, 2008)	Attention, working memory, processing speed, reliable digit span validity			

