Clinical and Functional Outcome Analyses: An additional goal of clinical and functional outcome data from this pilot RCT is to obtain effect size estimates to prepare for a future fully powered RCT. Because estimating effect sizes in small pilots is fraught with limitations and should not be used as a sole estimate (e.g., Kraemer et al., 2006), we will compare obtained effect sizes to those obtained for participants with PTSD in our CCT for mild TBI trial. We are not relying on the TBI data alone, however, because of the potentially significant differences in Veterans who do and do not have a history of TBI. Therefore, though we will conduct multivariate analyses of pilot data and examine the statistical significance of within and between group differences, we will focus on obtaining effect size estimates to prepare for a future trial. Because of the small sample size, we will examine data for trends to plan for future analyses in a fully powered RCT. To evaluate the proportion of Veterans with early discharges from CCT, we will conduct mixed models for binary outcomes. We will plan for an underpowered pilot trial, though will use the obtained effect sizes to estimate statistical power and needed sample size for the fully powered RCT RR&D Merit proposal in year 4 of the CDA. We will also use appropriate assumptions for planned statistical tests when calculating estimated power.

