Enrollment and Assessment Procedures: Prior to enrollment, interested Veterans will be prescreened. The study coordinator will conduct a medical record review to document cognitive symptoms, medical and psychiatric history, and recent treatments and medications. The Neurobehavioral Symptom Inventory (NSI) will be used as a screening tool to determine the presence of moderate or greater cognitive symptoms for eligibility purposes. A brief phone interview will ensure that Veterans are interested in participating and meet eligibility criteria. All participants will be screened to ensure their ability to comprehend study procedures, risks and benefits. We anticipate that up to 500 Veterans will need to be screened in order to achieve the desired sample size of 36-48 Veteran participants in the study. Veterans will be provided the opportunity to have the informed consent materials mailed to them. After the Veteran receives the informed consent materials, a trained study team member will call the Veteran to go through the informed consent procedures and answer any questions. If the Veteran chooses to participate, he or she will sign the informed consent documents and mail them back to [name] using a pre-addressed and stamped envelope. The study assessment will only be scheduled after the hard copy informed consent is received back from the Veteran. Following determination of eligibility, provision of informed consent, and enrollment into the pilot trial, Veterans will initiate the pilot RCT assessments, and, when assigned to the CCT condition, the 10-week CCT group intervention (weeks 2-11). Cognitive assessments and symptom questionnaires will be completed at baseline, post-treatment (approximately 3-months following baseline), and follow-up (6-months following baseline). Veterans will have the option to complete all study activities, including the 10-week CCT intervention and the 3 cognitive assessments via the VA's telehealth system, VA Video Connect (VVC), or via telephone.

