Participants will be at least 36 (and up to 48) Veterans weighted with more CCT participants (approximately 4-5 CCT groups with 6 Veterans each) than controls (12-18 TAU participants, grouped for randomization piloting purposes into 6-Veteran participants in each of 2 groups). Veterans of all genders, races, and ethnicities will be eligible for this study. We have estimated enrollment for gender, race, and ethnicity based on the recent CCT for mild TBI study, assuming similar demographic proportions. Eligibility will be established by current Mental Health or PTSD Clinic provider and CPRS chart review and will be confirmed by the Veteran during the initial phone call. Eligible Veterans (1) must meet DSM-5 criteria for PTSD based on PTSD or Mental Health Clinic intake assessment or PTSD diagnosis at most recent Mental Health/PTSD clinic visit if intake was completed over 6 months prior to study participation; (2) are patients in the PTSD specialty clinic or Mental Health clinic with a current mental health provider who is willing to provide TAU if randomized as such; (3) prior EBP treatment within the past 2 years confirmed by patients, their current Mental Health or PTSD clinic provider, and a review of CPRS records; (4) do not have a history of TBI of any severity; (5) are able to provide informed consent; (6) are English speaking; (7) are able to travel to the clinics for appointments; (8) do not have auditory or visual impairments that would compromise assessments; (9) do not meet criteria for a substance dependence disorder with less than 30 days abstinence; (10) do not meet criteria for bipolar disorder or psychotic disorders; (11) do not have active suicidal intent indicating significant clinical risk (which would suggest that a treatment specifically targeting this intent was indicated); (12) do not have a major medical condition likely to significantly impact cognitive functioning such as stroke, multiple sclerosis, Parkinson's, brain tumor, or congestive heart failure; (13) are not currently participating in any type of brain stimulation treatment; and (14) are between the ages of 18 to 75 years old. To maximize the generalizability of the study and ensure that we are testing CCT with a typical PTSD Veteran population, exclusion criteria are minimized (e.g., there are no medication exclusion criteria, and Veterans with comorbid depression or anxiety disorders will be included). Current cognitive functioning deficits are also required for participation, and chart review and NSI screening will be implemented for this study.

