
Informed Consent & HIPAA Authorization

For all studies, written informed consent will be obtained from all Veteran participants who attend in-person visits and electronic informed consent will be obtained through DocuSign for those Veterans who participate by phone or VVC. The consent process will be conducted by trained research team members. Eligible participants will be Veterans with a current diagnosis of PTSD who have been referred for PTSD mental health treatment in the VA Portland mental

11

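### Sessions attended is listed as a treatment moderator although it arises after randomisation, and the PTSD example is an entry criterion

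*Combined protocol and SAP*

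**What the plan says.** **Analysis.** The Clinical and Functional Outcome Analyses section plans multilevel models of change over time in CCT versus TAU, including everyone randomised by assigned arm, with ANOVA as a fallback. Its last sentence says that multilevel or repeated measures ANCOVA models will examine "potential moderators including validity tests, service connection status and percent, number of sessions attended, comorbid mental health diagnosis such as PTSD", along with demographic variables.

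**Attendance.** Under Feasibility and Acceptability: "Detailed records on recruitment, session attendance, and homework completion will be kept throughout the intervention". The Informed Consent & HIPAA Authorization section places randomisation after consent and the baseline assessment. Under Enrollment and Assessment Procedures, participants begin the trial assessments and, "when assigned to the CCT condition, the 10-week CCT group intervention (weeks 2-11"), the CCT sessions. The Intervention paragraph states that "TAU will consist of routine, weekly mental health psychotherapy". No section defines what counts as a session in the TAU arm. The outcome section also plans mixed models with the stated purpose "To evaluate the proportion of Veterans with early discharges from CCT", so incomplete attendance is foreseen.

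**PTSD.** Under Inclusion/Exclusion Criteria, eligible Veterans "must meet DSM-5 criteria for PTSD based on PTSD or Mental Health Clinic intake assessment", or must have the diagnosis at their latest clinic visit if intake was more than 6 months earlier. The consent section repeats this: "Eligible participants will be Veterans with a current diagnosis of PTSD". The criteria also state that "Veterans with comorbid depression or anxiety disorders will be included".

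**The concern.** A moderator of a randomised comparison should be fixed before assignment, so that the treatment contrast within each level is still protected by randomisation. Attendance does not meet that condition. It is partly a response to the assigned treatment, and it is shaped by things such as motivation, severity and stability that also bear on outcome. A positive attendance slope could be read as showing that CCT works better in those who attend, when it may only show that people with a better outlook attend more.

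PTSD is the index condition of this trial, not a comorbidity. A variable that takes one value in every participant cannot moderate anything and would drop out of the model.

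The stake is limited. The section says the team will look at trends in the pilot to plan later analyses, so a misread slope could be carried forward.

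**Working it through.** The plan gives no figure to reproduce here, so the check is whether the moderator term can be estimated and, if so, what it would mean.

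**Inputs.** Arm sizes come from Inclusion/Exclusion Criteria: 4 to 5 CCT groups of 6, so 24 to 30, and 12 to 18 in TAU. The extremes match the stated total: 24 + 12 = 36 and 30 + 18 = 48. The session values used are arbitrary; any values that vary within an arm give the same ranks.

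**Models.** The protocol does not write out the models. Moderation of the arm contrast needs at least an intercept, arm A, moderator M and A×M (4 terms). For change over time, add T, T×A, T×M and T×A×M (8 terms), with T×A×M as the term of interest.

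1. *Sessions, TAU coded 0.* In CCT, A = 1, so A×M = M. In TAU, both are 0. The two columns are identical: rank 4 − 1 = 3. With time, A×M = M and T×A×M = T×M: rank 8 − 2 = 6.
2. *Sessions, TAU visits counted.* M varies in both arms, so the design has full rank. The software returns an estimate, but M counts CCT sessions in one arm and psychotherapy visits in the other.
3. *PTSD by the entry definition.* M = 1 for all, so M equals the intercept and A×M = A: rank 4 − 2 = 2. With time, T×M = T and T×A×M = T×A are also duplicates: rank 8 − 4 = 4.
4. *Another diagnosis that varies in both arms.* Full rank.

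| Moderator | Rank of 4 | Rank of 8 | Moderation estimable? |
|---|---|---|---|
| Sessions, TAU = 0 | 3 | 6 | no |
| Sessions, TAU visits counted | 4 | 8 | yes, but not like for like |
| PTSD, entry definition | 2 | 4 | no |
| Other diagnosis, varying | 4 | 8 | yes |

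Results are the same at 24:12 and 30:18, and with 2 or 3 time points.

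**How easily attendance could mislead (illustration only).** Take 27 CCT participants, the midpoint of 24 and 30, and give attendance no effect on outcome. Let a shared prognostic factor produce an attendance–change correlation r. Test with t = r̂·√[(n − 2)/(1 − r̂²)], where r̂ is the sample correlation, against 2.06 (25 df, two-sided 5%). Over 4,000 simulated trials:

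| Assumed r | Significant slope |
|---|---|
| 0.2 | about 17% |
| 0.3 | about 34% |
| 0.5 | about 78% |

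The documents give no such correlation, so these values are assumptions and do not measure the bias in this trial.

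**The case against.** **PTSD need not mean the entry definition.** Entry rests on clinic records and follows earlier evidence-based psychotherapy. The rationale section reports that some Veterans lose the diagnosis after such treatment, and the baseline battery includes the MINI and PCL-5. MINI-defined status could therefore vary. This stands, with two limits: the sentence does not name the MINI, and the documents do not say how many would be negative.

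Precision is no reason to exclude such a term. At an assumed 30% MINI-negative, the interaction detectable with 80% power at two-sided 5% is about 2.3 SD (24:12) or 1.9 SD (30:18). For a diagnosis split 50:50 it is about 2.0 or 1.7 SD: the standard error is √(1/12 + 1/12 + 1/6 + 1/6) = 0.707 or √(1/15 + 1/15 + 1/9 + 1/9) = 0.596. Both calculations ignore clustering by CCT group and missing data.

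**The rank failure depends on coding.** With TAU coded 0, dropping the duplicate column leaves an estimable slope within CCT. That is true, but the slope is then a dose-response description in one arm and not moderation of CCT versus TAU. The timing problem remains under every coding.

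**Attendance may hardly vary.** The retention section says that everyone who began CCT in earlier research completed it, and that recent trials exceeded 90% retention. Completion and retention are not full attendance, and near-constant attendance would leave little to estimate. Neither point makes attendance a baseline variable.

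**The analyses are exploratory, in a pilot the protocol itself calls underpowered.** This is accepted, and it is why the point is rated minor.

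**Conclusion.** The concern holds, at minor severity. Sessions attended is not a valid moderator of CCT versus TAU under either coding: with TAU at zero the term cannot be estimated, and with TAU visits counted it can be estimated but not interpreted as moderation. This rests only on the timing of randomisation and on CCT sessions occurring in one arm.

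The category of comorbid diagnosis is sound; the fault is in its example. On the entry definition the PTSD interaction cannot be estimated. That conclusion depends on the definition and would not apply to a baseline MINI status that varied.

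No size can be put on the attendance bias from the documents. The intent-to-treat comparison, the feasibility criteria and the sample-size inputs for the next trial do not depend on these analyses.

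**What to change.** Reword the last sentence of the Clinical and Functional Outcome Analyses section so that:

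- moderators are limited to variables measured at baseline: validity tests, service connection, demographics, and comorbid diagnosis other than PTSD;
- the number of CCT sessions attended is summarised within the CCT arm as adherence, with a statement that any association with outcome is not read as causal.

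If PTSD is still of interest as a moderator, use the baseline PCL-5 score and report the interaction with its 95% confidence interval. The standard error is √(1/n₁ + 1/n₀): √(1/24 + 1/12) = 0.354 or √(1/30 + 1/18) = 0.298. The interval is about ±0.72 or ±0.60 outcome SD per SD of PCL-5, again ignoring clustering and missing data. If the team means MINI-defined status instead, the sentence should say so and fix it at baseline.

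The cost is one sentence. Attendance records, baseline assessments, the MINI and the PCL-5 are already planned.
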